**10.1.5. Data Protection**

Measures used to protect individual subject data include the following:

- Subjects will be assigned a unique identifier by the sponsor. Any subject records or datasets that are transferred to the sponsor will contain the identifier only; subject names or any information which would make the subject identifiable will not be transferred.
- The subject must be informed that their personal study-related data will be used by the sponsor in accordance with all applicable data protection laws. The level of disclosure must also be explained to the subject who will be required to give consent for their data to be used as described in the ICF.
- The subject must be informed that their medical records may be examined by Clinical Quality Assurance auditors or other authorized personnel appointed by the sponsor, by appropriate IRB / IEC members, and by inspectors from regulatory authorities.

**10.1.6. Dissemination of Clinical Study Information and Data**

- The sponsor will provide the relevant CSP information in public database(s) before or at commencement of the study. The sponsor may also provide study information for inclusion in national registries according to local regulatory requirements.
- Results of this study will be disclosed according to the relevant regulatory requirements. All publications in peer-reviewed medical journals resulting from this study will be listed in the original CSP registration record.

- This CSP will be made public following study completion with results posting in any applicable public registry (eg, ClinicalTrials.gov). Company confidential information within the CSP and personal protected data may be redacted as defined by regulatory authorities.

#### **10.1.7. Data Quality Assurance**

- All subject data relating to the study will be recorded either through the IRT system or on printed or electronic CRFs unless transmitted to the sponsor or delegate electronically (eg, laboratory data). The investigator is responsible for verifying that data entries are accurate and correct by physically or electronically signing the CRF.
- Guidance on completion of CRFs will be provided in the CRF Completion Guidelines.
- The investigator must permit study-related monitoring, audits, IRB / IEC review, and regulatory agency inspections and provide direct access to source data documents.
- The sponsor or delegate is responsible for the data management of this study including quality checks of the data.
- The sponsor assumes accountability for actions delegated to other individuals (eg, contract research organizations).
- Records and documents, including signed ICFs, pertaining to the conduct of this study must be retained by the investigator for the timeline outlined in the Clinical Trial Research Agreement.
- Quality tolerance limits, where appropriate, will be predefined in the Quality Risk Management Plan to identify systematic issues that can impact participant safety and / or reliability of study results. These predefined parameters will be monitored during the study and important deviations from the quality tolerance limits and remedial actions taken may be summarized in the clinical study report.
- Monitoring details describing strategy (eg, risk-based initiatives in operations and quality such as Risk-Based Quality Management), methods, responsibilities, and requirements, including handling of noncompliance issues and monitoring techniques (central, remote, or on-site monitoring), are provided in the Monitoring Plan and Quality Risk Management Plan.

#### **10.1.8. Committees Structure**

##### **10.1.8.1. Independent Data Monitoring Committee**

An IDMC will be established to monitor the safe conduct of the study. An IDMC charter outlines the roles and responsibilities of the committee and guides its operations. The IDMC will consist of independent clinical specialists in HAE, who also have experience in clinical trials. The IDMC responsibilities include the following:

- Review the safety data at planned intervals and identify if significant safety concerns arise during the study.
- Based on these reviews, provide recommendations regarding study conduct matters that affect safety.
- No success or futility thresholds will be set for the IDMC reviews.

- The sponsor will continue the study unless a safety issue is confirmed that warrants study termination.

The composition, activities, analyses, responsibilities, and timing of meetings of the IDMC will be described in the IDMC charter.

#### **10.1.9. Source Documents**

- Source documents provide evidence for the existence of the subject and substantiate the integrity of the data collected. Source documents are filed at the investigator's site.
- The definition of what constitutes source data can be found in the Clinical Trial Research Agreement.
- Data reported through the IRT system or entered into the CRF that are transcribed from source documents must be consistent with the source documents. If there are data discrepancies, the discrepancies must be explained. The investigator may need to request previous medical records or transfer records, depending on the study. Current medical records must also be available.
- The investigator must maintain accurate documentation (source data) to support the information entered into the CRF.

Study monitors will perform ongoing source data verification to confirm that data entered into the CRF by authorized site personnel are accurate, complete, and verifiable from source documents; that the safety and rights of subjects are being protected; and that the study is being conducted in accordance with the currently approved CSP and any other study agreements, ICH GCP, and all applicable regulatory requirements.

#### **10.1.10. Premature Site Closure and Study Termination**

The sponsor or delegate reserves the right to close the study site prematurely or terminate the study at any time for any reason at the sole discretion of the sponsor. Study sites will be closed upon study completion. A study site is considered closed when all required documents and study supplies have been collected and a study site closure visit has been performed.

Reasons for premature site closure include, but are not limited to, the following:

- Failure of the investigator to comply with the CSP, the requirements of the IRB / IEC or local health authorities, the sponsor's procedures, or GCP guidelines.
- Inadequate recruitment (evaluated after a reasonable amount of time) of subjects by the investigator.
- Enrollment target achieved earlier than expected.
- The reason for study termination may include, but is not limited to, discontinuation of investigational product development for any reason.
- If the study is terminated or suspended, the sponsor will promptly notify the investigators, the IRBs / IECs, the regulatory authorities, and any contract research organization(s) used in the study and provide the reason for termination or suspension, as specified by the applicable

regulatory requirements. The investigator will promptly inform the subject and should ensure that they are properly transitioned out of the study.

#### **10.1.11. Publication Policy**

The rights and obligations of investigators and the sponsor concerning any formal presentation or publication of data collected as a direct or indirect result of this study will be addressed specifically in the Clinical Trial Research Agreement for the study.

### **10.2. Adverse Events and Serious Adverse Events: Definitions and Procedures for Recording, Evaluating, Follow-up, and Reporting**

#### **10.2.1. Definitions**

##### **10.2.1.1. Adverse Event**

An AE is any untoward medical occurrence in a clinical study subject administered an investigational product and that does not necessarily have a causal relationship with this treatment. An AE can, therefore, be any unfavorable and unintended sign (including an abnormal, clinically significant laboratory finding), symptom, or disease temporally associated with the use of a medicinal (investigational) product, whether or not considered related to the medicinal (investigational) product.

The observation period for AEs is defined in [Section 10.2.4](#).

AEs may include the following:

- Exacerbation (ie, an increase in the frequency or severity) of a preexisting condition. Preexisting conditions should be recorded on the Medical History CRF and only reported as an AE if there is an increase in the frequency or severity of the condition during the study.
- A clinical event occurring after consent and before investigational product administration.
- Intercurrent illnesses with an onset after administration of investigational product.

AEs do not include the following:

- Events identified at [Screening](#) that meet exclusion criteria
- Medical or surgical procedures (the condition that leads to the procedure is the AE)
- Situations where an untoward medical occurrence has not taken place. For example:
  - Planned hospitalizations related to preexisting conditions that have not worsened
  - Hospitalizations that occur for procedures not due to an AE (eg, cosmetic surgery)
  - Hospitalizations for a diagnostic procedure where the hospital stay is less than 24 hours in duration or for normal management procedures (eg, chemotherapy)
- Overdose of investigational product or any concomitant therapy that does not result in any adverse signs or symptoms

For laboratory and other safety parameters (eg, vital signs), any instances of absolute values or changes at any visit after study start that are considered by the investigator as clinically

significant must be recorded on the AE CRF. In addition, at the investigator's discretion, any changes or trends over time in laboratory parameters may be recorded on the AE CRF if such changes or trends are considered to be clinically relevant, even if the absolute values are within the reference range.

Laboratory findings do not need to be reported as AEs in the following cases:

- Laboratory parameters already beyond the reference range at Screening, unless a further increase / decrease can be considered an exacerbation of a preexisting condition.
- Abnormal laboratory parameters caused by mechanical or physical influences on the blood sample (eg, in vitro hemolysis) and flagged as such by the laboratory in the laboratory report.
- Abnormal parameters that are obviously biologically implausible (eg, values that are incompatible with life or outside the measuring range).
- An abnormal laboratory value that cannot be confirmed after repeat analysis, preferably in the same laboratory (ie, the previous result could be marked as not valid and should not necessarily be reported as an AE).

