### 3. OBJECTIVES AND ENDPOINTS

**Table 2: Objectives and Endpoints**

Objective	Endpoint	Summary Measure
Primary		
The primary objectives of the study are to evaluate the safety and PK of SC administration of CSL312 in the prophylactic treatment of pediatric subjects with C1-INH HAE.	TEAEs	Number of subjects, percentage of subjects, and number of events as well as the event rates per injection and per subject year
	PK parameters after SC administration of CSL312 at steady state: 
 
• <math>C_{max}</math>
 
• <math>C_{trough}</math>
 
• <math>T_{max}</math>
 
	
 
• Mean (SD) and geometric mean (geometric CV%) for all PK parameters except for <math>T_{max}</math>
 
• Median (minimum, maximum) for <math>T_{max}</math>
 

Secondary		
The secondary objectives of this study are to evaluate efficacy, PD, and safety of CSL312 in the prophylactic treatment of pediatric subjects with C1-INH HAE.	
 
• Time-normalized number of HAE attacks
 
• Time-normalized number of HAE attacks treated with on-demand treatment
 
• Time-normalized number of moderate and / or severe HAE attacks
 
• Percentage reduction in the time-normalized number of HAE attacks
 
	
 
• The time-normalized number (per month and year) of HAE attacks, of HAE attacks treated with on-demand treatment, and of moderate and / or severe attacks on treatment, respectively
 
• The percentage reduction and the number of subjects experiencing at least <math>\geq 50\%</math>, <math>\geq 70\%</math>, <math>\geq 90\%</math>, or equal to 100% (attack-free) reduction in the time-normalized number of HAE attacks on treatment compared to their time-normalized number of HAE attacks documented in medical records
 

Objective	Endpoint	Summary Measure
	
 
• SAEs
 
• Deaths
 
• Related TEAEs
 
• TEAEs leading to study discontinuation
 
• TEAEs in each severity category
 
• Anti-CSL312 antibodies
 
• Laboratory findings reported as AEs
 
• AESIs (severe hypersensitivity including anaphylaxis)
 
	The number and percentage of subjects experiencing the specified safety events on treatment as well as the event rates per injection and per subject year

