### 8.3.2. Clinical Safety Laboratory Assessments

- The investigator must review the laboratory report, document this review, and record any clinically significant changes occurring during the study as an AE. The laboratory reports must be filed with the source documents. Refer to [Table 7](#) for the assessment of severity of AEs associated with laboratory results.
- Abnormal laboratory findings associated with the underlying disease are not considered clinically significant unless judged by the investigator to be more severe than expected for the subject's condition.
- All laboratory tests with values considered clinically significantly abnormal during participation in the study or within after the last dose of investigational product should be repeated until the values return to normal or baseline or are no longer considered clinically significant by the investigator or sponsor's medical monitor.
  - If clinically significant values do not return to normal / baseline within a time judged reasonable by the investigator, the etiology should be identified, and the sponsor notified.
  - All protocol-required laboratory tests must be conducted in accordance with the Laboratory Manual and the Schedule of Activities ([Section 1.3](#)).
  - If laboratory values from nonprotocol-specified laboratory tests performed at the institution's local laboratory require a change in subject management or are considered clinically significant by the investigator (eg, SAE or AE or dose modification), then the results must be recorded in the subject's source documents.

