7.2.5 Multiple Assessments

All data will be reported according to the nominal visit date for which they were reported (that is, no visit windows will be applied during dataset creation and the visit will not be re-allocated if the actual visit date deviates from the planned date according to the visit schedule in the protocol). Unscheduled data will not be included in by-visit summaries, but may contribute to the Baseline value, the End of Study (EoS) value, or best/worst case value (e.g., shift tables) and will appear in listings.

If a laboratory sample was repeated due to technical problems the results from the valid sample(s) for this visit will be used in the analysis. If a laboratory sample was repeated as safety follow-up to monitor abnormal values of the initial sample, the initial sample (revealing the abnormal values) of this visit will be used in the analysis.

Data from all assessments (scheduled and unscheduled), including multiple assessments, will be included in listings.

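### Protocol 10.2.1.1 treats a laboratory result outside the measuring range as an example of an implausible value that need not be an AE, and does not reconcile this with the rule that clinically significant values must be recorded

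*Protocol*

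**What the plan says.** Protocol 10.2.1.1 first sets a mandatory rule. For laboratory and other safety parameters, "any instances of absolute values or changes at any visit after study start that are considered by the investigator as clinically" significant must go on the AE form. Protocol 8.3.2 repeats the duty: the investigator must review each laboratory report and record clinically significant changes as AEs.

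Section 10.2.1.1 then gives a list of exceptions, introduced by "Laboratory findings do not need to be reported as AEs in the following cases". Two of its four cases matter here:

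- The case on implausible results reads "Abnormal parameters that are obviously biologically implausible (eg, values that are incompatible with life or outside the measuring range").
- The case on non-confirmation, which closes the list, reads "An abnormal laboratory value that cannot be confirmed after repeat analysis, preferably in the same laboratory". The bullet adds that the earlier result could be marked not valid and "should not necessarily be reported as an AE".

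Protocol Table 2 names "Laboratory findings reported as AEs" as a secondary safety endpoint. TEAEs are the primary safety endpoint, summarized as a rate per subject year (Protocol 9.4.3.1).

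For repeated samples, SAP 7.2.5 separates two situations. After a technical problem, the valid sample is used. After a safety repeat to monitor abnormal values, "the initial sample (revealing the abnormal values) of this visit will be used in the analysis".

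**The concern.** The measuring-range example mixes two different things. A value incompatible with life points to an error. A value outside an assay's range says only that the instrument could not put a number on it; the true value may be very high or very low. By offering the second as an example of the first, the protocol tells sites that an off-scale result may go unreported, although such a result can be the one a safety rule most needs to keep. Coagulation is the natural place for this to matter: CSL312 blocks FXIIa, which Protocol 2.1 links to a procoagulant pathway, and Protocol Table 6 includes aPTT, PT / INR and D-dimer in the safety panel.

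The non-confirmation case is looser than it needs to be. Repeat analysis could mean a second run of the same tube, which tests whether the first result was an error. It could also mean a new draw, which partly tests whether the abnormality has passed. Only the first is a reason to call the original result invalid.

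Both cases can only lower AE counts. They are applied by unblinded investigators (Protocol 6.4.2) in a study without a control group, so no comparator arm shares the omission.

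**Working it through.** The plan states no figure on this point, so the check is mainly a comparison of texts.

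**1. Does the exception overlap the mandatory rule?** The mandatory rule turns on clinical significance as judged by the investigator. The exceptions turn on implausibility or non-confirmation. A result can meet both conditions: an off-scale coagulation value may be clinically significant and also match the measuring-range example. The exceptions follow the rule in the same section and can be read as carve-outs from it. Neither 10.2.1.1 nor 8.3.2 says which prevails.

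**2. What does repeat analysis mean?** The bullet sets no specimen, no interval and only a preference for the same laboratory. In Protocol 8.3.2, tests with clinically significant abnormal values "should be repeated until the values return to normal or baseline or are no longer considered clinically significant by the investigator". That use of repeating plainly involves new samples, so a site could carry that meaning into 10.2.1.1.

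**3. Which outputs depend on AE reporting?**

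- Dependent: the TEAE rate and TEAE percentages (SAP 10.2.2); the secondary endpoint on laboratory AEs; the table of TEAEs related to clinically significant laboratory abnormalities (SAP 10.2.3); and the count of subjects with clinically significant laboratory findings related to a TEAE (SAP 10.3).
- Not dependent: the listings of all laboratory results, scheduled and unscheduled, and the separate listing of abnormal results (SAP 10.3).
- By-visit laboratory summaries do not depend on AE status either. However, SAP 10.3 gives no rule for how an off-scale value enters a mean or median, so the listings are the surer place to find it.

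**4. Does the SAP remove a real abnormality from the laboratory data?** SAP 7.2.5 decides by the reason for the repeat. A repeat taken because the first value was abnormal is safety follow-up, and the first value is kept.

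**5. Illustrative size.** Inputs: about 20 subjects enrolled and at least 15 completing (Protocol 4.1); End of Treatment on Day 361 (Protocol 1.3); 365.25 days per year (SAP 7.2.2). Suppose one child's single laboratory AE is not reported.

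- Percentage of subjects: 1/20 = 5.0 points; with 15 subjects, 1/15 = 6.7 points.
- Subject years: 20 × 361 / 365.25 = 19.8.
- TEAE rate: 1 / 19.8 = about 0.05 per subject year.

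The tables are also given by dosing regimen. The documents do not state the planned split, but one child weighs more in either group than in the total.

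**The case against.** The strongest reply is that the wording is narrower than it looks. The case covers only values that are obviously biologically implausible, and the measuring-range phrase is an example under that condition. If an extreme coagulation value is plausible on this drug, it fails the test and stays reportable. The list is also permissive, and two passages make recording of clinically significant values mandatory. The same section even allows trends within the reference range to be recorded as AEs, which widens reporting.

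Much of this stands. A reader might infer that every result outside the measuring range is exempt; the implausibility condition does not support that. The reply does not remove the defect, though, because the example itself tells a site that an off-scale result meets the condition.

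On repeats, a reader might infer from Protocol 8.3.2 that a real abnormality is cancelled once a later sample is normal. The text does not say so. Those repeats follow values already judged clinically significant, which the same section requires to be recorded as AEs. The references in 10.2.1.1 to the same laboratory and to a result marked not valid read most naturally as an error check. This part is mainly a clarification.

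A reader might also infer that extreme values vanish from the safety analysis, or that SAP 7.2.5 lets a normal repeat replace them. Neither is supported: all results are listed, and the initial abnormal sample is kept for safety repeats. Treating such a repeat as technical would go against the SAP's own distinction.

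Finally, the Laboratory Manual and the CRF completion guideline may say how off-scale results are handled. They are not among the documents reviewed, and the protocol wording should not depend on them.

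**Conclusion.** Wrong as written, but minor. The measuring-range example is a stated rule that can exclude true extreme values from AE reporting, and the plan does not say that the mandatory rule overrides it. The undefined repeat analysis adds a smaller ambiguity. The effect is limited to outputs built on AE reporting and runs in one direction, towards fewer events.

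The size cannot be stated, because the documents give no assay limits, no interval for repeats and no expected frequency of such results. The 5-point and 0.05-per-subject-year figures show only what one omitted child or event would do. They assume 20 treated subjects and, for the rate, 361 days each; they say nothing about how often it would happen. The conclusion rests on one general premise: that a result beyond an assay limit can be real.

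**What to change.** Amend Protocol 10.2.1.1 in four places:

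1. Delete the phrase on the measuring range from the implausible-value case.
2. State that off-scale results are recorded as > or < the assay limit and judged for clinical significance like any other value.
3. Limit the non-confirmation case to re-analysis of the same specimen, or to a documented sample or assay error.
4. State that the duty to record clinically significant findings prevails over the list of exceptions.

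SAP 7.2.5 can stay as it is. The CRF completion guideline should carry the same wording. The cost is a short text change, and a few more laboratory AEs may be reported.
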